11.3 PRE-TREATMENT DEVICE USE ONBOARDING

Participants in the EaseVRx and Sham VR conditions will receive a PICO G2 4K headset with either EaseVRx or Sham content along with detailed instructions that will help them familiarize themselves with the hardware and software components. Telephonic and email technical support from study staff will be available to advise participants having trouble using the equipment. The participant will receive a reminder email to confirm VR headset receipt within 48 hours after FedEx tracking number was sent.

11.4 TREATMENT PHASE (WEEKS 0-8) & EXTENDED USE PERIOD (WEEKS 9-16)

Weeks 1-8: All participants will be instructed to use VR once a day for these 8 weeks. Research staff will monitor participants' progress through twice weekly BPI surveys and provide guided technical support. Device use can be monitored on a weekly basis for those participants who connect the device to Wi-Fi.

Weeks 9-16: For the 2 groups that are assigned to the arms with an extended 56-day on-demand period, participants will have the option of accessing VR for an additional 8-week period at their discretion. These groups will be instructed to use VR on an as-needed basis (i.e., there will be no set requirement for daily use as with the initial 8-week treatment phase).

11.5 DAY 56

On Day 56, participants will complete their treatment phase and will be prompted to log onto the Curebase portal and complete the following assessments:

- Brief Pain Inventory - intensity/interference
- Oswestry Disability Index
- PROMIS Sleep Disturbance
- PROMIS Depression
- PROMIS Anxiety
- Participant Satisfaction
- Participant's Global Impression of Change Scale (PGIC)

- Concerns About Pain (CAP-6) Scale
- System Usability Scale (SUS)
- Behavioral Skills Use
- EaseVRx User Experience Questionnaire (and at week 16 in two arms with on demand Library)

Data Completion Reminders: Participants will be sent a reminder if they have not submitted data approximately 1 hour after starting a survey. Participants will also receive a reminder email or text message if they do not submit data approximately 24 hours after starting a survey. Research staff will make up to 3 call attempts to contact the participant to help get these surveys completed.

Twenty-four hours after completing the surveys listed above, participants will be contacted with information about completing an optional incentivized set of surveys that include the following:

- Pain Self-Efficacy Questionnaire (PSEQ-10)
- Multidimensional Assessment of Interoceptive Awareness (Version 2)
- Multidimensional Health Locus of Control

Reminders will be sent approximately 1 hour and 24 hours after starting a survey to encourage optional survey completion.

11.6 POST-TREATMENT DATA COLLECTION

After Day 56, participants will be prompted to log onto the Curebase portal and complete the following assessments at 4-weeks, 8-weeks, 12-weeks, 6-months, 12-months, 18-months, and 24-months post-treatment:

- Brief Pain Inventory - intensity/interference
- Oswestry Disability Index
- PROMIS Sleep Disturbance
- PROMIS Depression
- PROMIS Anxiety
- participant's Global Impression of Change Scale (PGIC)
- Concerns About Pain (CAP-6) Scale
- Behavioral Skills Use

Data Completion Reminders: Participants will be sent a reminder if they have not submitted data approximately 1 hour after starting a survey. Participants will also receive a reminder email or text message if they do not submit data approximately 24 hours after starting a survey. Research staff will make up to 3 call attempts to contact the participant to help get these surveys completed.

Twenty-four hours after completing the surveys listed above, participants will be contacted with information about completing an optional incentivized set of surveys that include the following:

- Pain Self-Efficacy Questionnaire (PSEQ-10)
- Multidimensional Assessment of Interoceptive Awareness (Version 2)
- Multidimensional Health Locus of Control

Reminders will be sent approximately 1 hour and 24 hours after starting a survey to encourage optional survey completion.

11.7 HEALTHCARE UTILIZATION ANALYSIS

To assess resource use associated with CLBP, participants' data will be run through a secure Datavant matching process to be linked to their healthcare claims data if it is available in the Komodo data set. The claims will provide descriptive characterizations of resource use and costs associated with CLBP. For participant-level changes in resource use, and for comparisons between study arms, only the participants with complete claims files will be assessed. Claims-matched data will capture all interactions with the healthcare system that generate an insurance claim record, which includes such things as physician visits, interventions such as steroid injections, surgery or physical therapy, emergent use of services, medications, and diagnostic procedures. Claims adjudication often lags a few months, so the most robust analyses of utilization will be performed about 6 months after the time point of interest (check with Komodo on adjudication/timing implications). Health economic modeling will be performed after 1 year to assess the cost and economic outcomes of the EaseVRx intervention.

The Komodo claims data provides a real-world source of utilization and cost parameters associated with claims of CLBP. As such, it can be used more broadly to either compare the study participants' resource use and costs to the broader population of participants with CLBP, or a "synthetic arm" can be constructed using available demographic data to match any of the study arms.

Additional details are detailed in a standalone Healthcare Utilization Analysis Plan.

12 STUDY INTERVENTION

12.1 MEASURES TO MINIMIZE BIAS: RANDOMIZATION AND BLINDING

The primary endpoint of this study will be collected via Electronic Data Capture and securely transmitted to the Database. Curebase will maintain the database and be responsible for all aspects of data management.

Participants, study statisticians and investigators will be blinded to treatment group assignment until after the last subject contributes their primary outcome at week 8 . Prior to the primary analysis, the database will be officially locked and signed off by the Sponsor and key stakeholders. Study participants will remain blinded to treatment group assignment until study completion.

12.2 STUDY INTERVENTION COMPLIANCE

Compliance to the treatment protocol will be monitored using remote data uploads of survey logs if a headset is connected to Wi-Fi by the participant. For participants who do not connect their headset to Wi-Fi, compliance will be assessed post-intervention when the headset has been returned.

13 STUDY INTERVENTION DISCONTINUATION AND PARTICIPANT DISCONTINUATION/WITHDRAWAL

13.1 DISCONTINUATION OF STUDY INTERVENTION

A small proportion of participants may find the headset uncomfortable, the VR experiences ineffective, or find themselves not using the device and wish to withdraw. Participants who report moderate to severe adverse events that prevent them from using the program will be discontinued. Discontinuation from the use of the VR program or Sham VR will not automatically trigger discontinuation from the study, and remaining study procedures should be completed as indicated by the study protocol. If a clinically significant finding is identified (including, but not limited to changes from baseline) after enrollment, the investigator or qualified designee will determine if any change in participant management is needed. Any new clinically relevant finding will be recorded as an adverse event (AE).

13.2 PARTICIPANT DISCONTINUATION/WITHDRAWAL FROM THE STUDY

Participants are free to withdraw from participation in the study at any time and for any reason. A member of the research team will ask the participant for the reason for their withdrawal and will record all information regarding the participant discontinuation in their study records.

An investigator may also discontinue or withdraw a participant from the study for the following reasons:

- If any serious to severe adverse event (AE) or other medical condition or situation occurs such that continued participation in the study would not be in the best interest of the participant
 - Participants who experience an SAE due to an undisclosed condition that would have prevented trial eligibility will be discontinued from the study and will be documented as an eligibility deviation.
- Disease progression which requires discontinuation of the study intervention
- If the participant meets an exclusion criterion (either newly developed or not previously recognized) that precludes further study participation
- Any other problem deemed by the Investigator to be sufficient to cause discontinuation.

The reason for participant discontinuation from the study will be recorded.

13.3 LOST TO FOLLOW-UP

A participant will be considered lost to follow-up if he or she fails to complete two or more consecutive surveys and is unable to be contacted by the study site staff. Before a participant is deemed lost to

follow-up, the investigator or designee will make every effort to regain contact with the participant (where possible, 3 telephone calls). If participants are not reached in these attempts, they will receive a final email asking them to complete a discontinuation form. These contact attempts and any discontinuation will be documented. Should the participant continue to be unreachable, he or she will be considered to have withdrawn from the study with a primary reason of lost to follow-up.

13.4 EQUIPMENT RETURN

Participants will not be financially responsible for damage to, or loss of, equipment loaned to participants by the research team during this study. However, if they are not able to return the headset at the end of the VR treatment, regardless of its condition, then they will not be eligible to receive their honorarium payment. Reminders will be sent via email and text at the end of VR treatment period (8-weeks or 16-weeks), and a call will be made if the device still is not returned after multiple reminders during a 14-day period. If the device is not returned, then the study team will document the reason for the participant not returning the device from the phone call (e.g., lost).

14 STUDY ASSESSMENTS

14.1 EFFICACY ASSESSMENTS

Primary Outcome

The primary outcome for this study will be the BPI questionnaire. The BPI questionnaire is a validated instrument with good content validity, construct validity, and reliability in participants with chronic pain. The range of scores are from 0-10. The BPI contains a single item related to pain intensity and 7 items related to pain interference. The BPI pain interference score is the mean of seven questions that assess pain interference on general activity, mood, walking ability, normal work, relations with other people, sleep, and enjoyment of life. The higher the score the greater the impact of chronic pain on the participant.

Secondary Outcomes

Secondary outcomes include the Oswestry Disability Index score (ODI v2.1b), PROMIS Sleep Disturbance, PROMIS Depression, PROMIS Anxiety, and participant Satisfaction that will be evaluated before the intervention, immediately following the intervention (Day 56 in all arms), 4-weeks post-treatment, 8-weeks post-treatment, 12-weeks post-treatment, 6 months post-treatment, 12 months post-treatment, 18 months post-treatment, and 24 months post-treatment. participant Satisfaction will be evaluated on Day 56.

- **Oswestry Disability Index**

- The Oswestry Disability Index (also known as the Oswestry Low Back Pain Disability Questionnaire) is a tool that researchers and disability evaluators use to measure a participant's functional disability. The test is considered the 'gold standard' of low back

functional outcome tools. The *tool is well validated with excellent content validity, construct validity and reliability.*

- **PROMIS Scales Sleep Disturbance, Depression & Anxiety**

- For participants with chronic pain, sleep quality is often diminished, and participants seek return to normal function. The PROMIS® short-form scales are widely- validated instruments with excellent content validity, construct validity, and reliability in participants with spinal disorders and other conditions marked by diminished mobility. The sleep disturbance scale assesses perceptions of sleep quality, including perceived difficulties and concerns with getting to sleep or staying asleep, as well as perceptions of the adequacy of and satisfaction with sleep. The depression scale assesses the pure domain of depression in individuals aged 18 and older. The anxiety scale assesses the pure domain of anxiety in individuals aged 18 and older. All PROMIS® measures use a 7-day recall period reflecting the previous week's health status.

- **Virtual Reality Sickness Questionnaire**

- The Virtual Reality Sickness Questionnaire was developed for use as a motion sickness measurement index specialized for virtual reality environments. The 12 items measure such symptoms as dizziness and nausea with four response options (None to Severe).

- **Participant Satisfaction** (adverse effects and recommendations)

- A custom survey was created to assess satisfaction with our VR program. Topics include device usability, enjoyment or difficulties, and likelihood to continue treatment.

Tertiary / Exploratory Outcomes

- **Participant's Global Impression of Change Scale (PGIC)**

- This single item questionnaire is validated for use in studies to compare participant satisfaction between different treatment assignments.

- **Concerns About Pain (CAP-6) Scale**

- This six-item scale represents the first item response theory-based item bank of pain catastrophizing. The measure is intended for clinicians interested in improving outcomes of participants with chronic pain and for researchers who study impact of and treatment interventions aimed at reducing pain catastrophizing.

- **Systems Usability Scale (SUS)**

- The System Usability Scale (SUS) provides a reliable tool for measuring the usability of our VR program. It consists of a 10-item questionnaire with five response options (Strongly disagree to Strongly agree).

- **Behavioral Skills Use**

- One major goal of the skills-based VR intervention (EaseVRx) is to facilitate the development of behavioral coping strategies in chronic pain sufferers that can be utilized outside of the VR headset. The research team has constructed a survey to assess the development of these skills. Specifically, participants will be asked whether they can

manage their pain outside of the VR headset using deep breathing, releasing unhelpful thoughts, redirecting attention, and self-compassion coping behaviors.

- **EaseVRx User Experience Questionnaire**
 - This is a questionnaire constructed to better understand the user experience, usefulness, and participant satisfaction with the VR therapeutic program and some of its features. It is a 19-multiple-choice-item questionnaire with 6 optional open-ended questions. This questionnaire will only be presented to participants in the skills based EaseVRx conditions.
- **Pain Self-Efficacy Questionnaire (PSEQ-10)**
 - The Pain Self-Efficacy Questionnaire (PSEQ-10) is a validated instrument used to assess participants' confidence in their ability to carry out their daily activities. The 10-item questionnaire asks participants to rate their confidence from 0 to 6 corresponding to not at all confident to completely confident.
- **Multidimensional Assessment of Interoceptive Awareness (Version 2)**
 - The Multidimensional Assessment of Interoceptive Awareness (MAIA-II) will be used to evaluate how interoceptive awareness relates to the other study's outcome measures by assessing participants' bodily sensation awareness. It consists of a 37-item questionnaire with 6 response options (never to always) for 8 state traits (e.g., noticing, body listening).
- **Multidimensional Health Locus of Control (MHLC-C)**
 - The Multidimensional Health Locus of Control (MHLC-C) will be used to help characterize participants, their health-related behaviors, and response to treatment. It is an 18-item scale evaluating health locus of control with four subscales: internal, doctors, chance, and other people.
- **Discontinuation of Treatment Questionnaire**
 - The Discontinuation of Treatment Questionnaire will only be used if a moderate adverse event occurs. This will give the participants the option to discontinue from the study and may pinpoint cause of discomfort, if any.

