6.2 SCHEDULE OF ACTIVITIES (SoA)

VISITS	re-Treatment		Treatment		Post-Treatment (PT)						
	Day - 10 ¹	Day -9 to 0	Wks. 1-8	Day 56	4 Wks. (84 +7 days) ¹	8 Wks. (112 +7 days) ¹	12 wks. (140 +7 days) ¹	6 months (238 +30 days) ¹	12 months (420 +30 days) ¹	18 months (602 +30 days) ¹	24 months (784 +30 days) ¹
Pre-Screener	X										
Suicidality Screener - 9th item of PHQ-9	X										
Demographic survey	X										
Informed Consent via Curebase	X										
Identity Verification	X										
Brief Pain Inventory (BPI) pain intensity/interference	X	X ²	X ³	X	X	X	X	X	X	X	X
Oswestry Disability Index	X			X	X	X	X	X	X	X	X
PROMIS Sleep Disturbance	X			X	X	X	X	X	X	X	X
PROMIS Depression	X			X	X	X	X	X	X	X	X
PROMIS Anxiety	X			X	X	X	X	X	X	X	X
Concerns About Pain (CAP-6) Scale	X			X	X	X	X	X	X	X	X
Behavioral Skills Use	X			X	X	X	X	X	X	X	X
Participant's Global Impression of Change Scale (PGIC)				X	X	X	X	X	X	X	X
Pain Self-Efficacy Questionnaire (PSEQ-10)	X ¹			X ¹	X ¹	X ¹	X ¹	X ¹	X ¹	X ¹	X ¹
Multidimensional Assessment of Interoceptive Awareness (Ver 2)	X ¹			X ¹	X ¹	X ¹	X ¹	X ¹	X ¹	X ¹	X ¹
Multidimensional Health Locus of Control	X ¹			X ¹	X ¹	X ¹	X ¹	X ¹	X ¹	X ¹	X ¹
VR Sickness Questionnaire		X ⁴	X ⁴	X ⁴	X ⁴						
participant Satisfaction			X								
System Usability Scale (SUS)			X								
Benefits Screening								X			
Shipping Address Survey	X										
EaseVRx User Experience Questionnaire			X			X ⁵					
Randomization (performed within Curebase portal)		X									
Ship Intervention kit to participants		X									
Technical onboarding	X										
Record VR compliance/use data ⁶		X	X	X ⁵	X ⁵						
Collect study intervention kit							X				
Perceived Treatment Assignment			X								
Healthcare utilization data analysis			X ⁷	X ⁷	X ⁷	X ⁷	X ⁷	X ⁷	X ⁷	X ⁷	X ⁷

¹ OPTIONAL survey offered next day.

² Two out of five BPI survey instances to be completed over 9-day pre-intervention period.

³ Research staff will monitor participants' progress through twice weekly BPI surveys.

⁴ VR Sickness Questionnaire will be administered once per week during treatment and once per week for the 16-week arms.

⁵ For participants assigned to extended 56-day on-demand period only.

⁶ Device use to be monitored on a weekly basis when participants connect the device to Wi-Fi. For participants who do not connect their headset to Wi-Fi, compliance will be assessed post-intervention when the headset has been returned.

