- Behavioral Skills Use: Baseline, Day 56, 4-weeks post-treatment, 8-weeks post-treatment, 12-weeks post-treatment, 6 months post-treatment, 12 months post-treatment, 18 months post-treatment, and 24 months post-treatment
- Product Enhancement recommendations: Day 56 for the EaseVRx-8w and EaseVRx-8w plus extended on-demand groups, and at 8-weeks post-treatment for the EaseVRx-8w plus extended on-demand group
- Treatment Compliance: End of treatment for the EaseVRx and Sham VR groups and 8-weeks post treatment for the EaseVRx plus on demand Library and Sham VR plus on demand Library groups.

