9.4 END OF STUDY DEFINITION

The study will be considered complete at the time that the last participant performs the last survey. Participants are expected to remain in the study for 24 months after undergoing their respective treatment period (8 or 16 weeks). Participants who complete their 24-month follow-up survey (see Schedule of Activities, Section 5.2.) will be considered to have completed study participation.

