14.2 OTHER ASSESSMENTS

- **Treatment Compliance:**
 - Data related to the frequency and length of time using the intervention will be stored on the virtual reality headset for the entire 8-week or 16-week period (depending upon the participant's arm in the study). The data will be sent back to the research team via connection to the participant's phone using mobile data, or when the headset is returned.
- **Perceived Treatment assignment Question:**
 - At the end of treatment for all groups, the research team will evaluate how expectations relate to our program's outcomes by assessing participants' beliefs about their group

assignments. The research team will also ask participants to report which VR program condition they believed they participated in.

- **Benefits Screening:**

- At 12 months participants will be asked if they are currently receiving or have previously received/petitioned for disability or worker's compensation benefits. This will allow the research team to account for possible motivating factors for participants to report increased pain or have increased healthcare utilization during the course of the study.

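### The protocol's sections disagree on which arms get the product-named Day 56 questionnaire, and as an EaseVRx-only form it could reveal active assignment before 24 months of self-reported follow-up

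*Protocol*

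**What the plan says.** Protocol 14.1 describes a 19-item questionnaire, with optional open questions, on the experience and usefulness of the VR program and some of its features. It adds: "This questionnaire will only be presented to participants in the skills based EaseVRx conditions".

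Protocol 11.5 introduces the Day 56 session without distinguishing arms: "On Day 56, participants will complete their treatment phase and will be prompted to log onto the Curebase portal". The list that follows starts with the BPI and ends with "EaseVRx User Experience Questionnaire (and at week 16 in two arms with on demand Library". One of the two on-demand arms is Sham.

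The Schedule of Activities (6.2) attaches footnote 5 to the later administration: "For participants assigned to extended 56-day on-demand period only". It draws no line between EaseVRx and Sham.

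Protocol 9.1 lists what may be the same instrument under another name: "Product Enhancement recommendations: Day 56 for the EaseVRx-8w and EaseVRx-8w plus extended on-demand groups". It repeats that item at 8 weeks post-treatment in the EaseVRx on-demand arm only.

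On blinding, Protocol 12.1 and SAP 1.6 say: "Study participants will remain blinded to treatment group assignment until study completion". Protocol 9.4 defines the end point of that commitment: "The study will be considered complete at the time that the last participant performs the last survey".

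Protocol 14.2 places the blinding check at end of treatment for all groups: "The research team will also ask participants to report which VR program condition they believed they participated in". The 11.5 list does not include it.

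**The concern.** The primary and main secondary endpoints, and the follow-up questionnaires, are answered by the participant at home. Participant blinding is therefore the chief protection against biased reporting, and Protocol 7.4 gives the blinding problem in VR studies as a reason for choosing this sham.

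As 14.1 has it, half the participants receive a form bearing the name of the product under test at the end of treatment, and the other half do not. A participant who sees the name and takes it to mean the active program has been given a cue. Knowledge of active assignment would be expected to push self-reports in favour of EaseVRx.

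Two things are mainly exposed. The first is the set of self-reported outcomes after Day 56. SAP 2.9 defines long-term estimands on these, and SAP 2.8.1 raises the sample size partly to test 30% response at longer time points. The second is the perceived-assignment item, which can show whether blinding held during treatment only if it is answered before any such cue.

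**Working it through.** The point rests mainly on comparing sections; the counts below are simple arithmetic.

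**1. Who receives the form.** With 1:1:1:1 allocation of about 1000, each arm has 1000 / 4 = 250.

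- 14.1: EaseVRx arms only, so 2 × 250 = 500 at Day 56 and no Sham participants at any time.
- 9.1, if its item is the same form: 500 at Day 56, then 250 at 8 weeks post-treatment, all EaseVRx. Equating the two is an inference.
- 11.5, read literally: all 1000 at Day 56, then 2 × 250 = 500 at week 16, of whom 250 are Sham.
- 6.2, footnote 5: 500 at 8 weeks post-treatment, with no EaseVRx limit.

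Week 16 and 8 weeks post-treatment are the same occasion (Day 56 + 56 = Day 112), so 14.1 and 9.1 differ from 11.5 and 6.2 on the same administration. The survey portal cannot be set up to satisfy both 14.1 and 11.5.

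**2. How much follow-up lies after the form.** The post-treatment visits are nominally at Days 84, 112, 140, 238, 420, 602 and 784: seven visits over 784 − 56 = 728 days. All fall within the period in which participants are to remain blinded.

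**3. Order within end of treatment.** The BPI is first in the 11.5 list and the questionnaire last, but the list is not stated to be a sequence. The perceived-assignment item is not in it. Unfinished surveys are chased by reminders and up to three calls, and SAP 2.4 keeps all pain values even when out of window. A BPI completed after the questionnaire would therefore still count.

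**4. What the cue requires.** Under 14.1, the product name must be visible to the participant and understood as the active program. Under 11.5, the title goes to every arm at Day 56 and so does not separate them; only the item content could, and that is not given.

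**5. Illustration of the conditional risk to the BPI.** This uses an assumed reporting shift that is not in the documents. The model is that of SAP 2.8.1: bivariate normal changes with the Table 2 SDs (EaseVRx 1.64 and 1.99, Sham 1.68 and 1.97) and correlations (0.76 and 0.77), two-sample t-tests, and Hochberg at one-sided 0.025 (success if the larger p < 0.025 or the smaller p < 0.0125). With the Table 2 means and 120 per group it gives 97.8% power over 10,000 trials, consistent with the SAP's figure of more than 95%.

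Next, both groups were given the Sham mean changes (−1.21 and −1.82), so there is no true effect. A shift was added to both scores for every EaseVRx participant, with 1000 × 0.85 / 2 = 425 per pooled group and 4,000 trials per setting:

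| Assumed shift (points) | Trials declared a success |
|---|---|
| 0 | 2.2% |
| 0.1 | 12.0% |
| 0.2 | 38.7% |
| 0.3 | 72.0% |
| 0.4 | 92.4% |

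This shows how sensitive a trial of this size is to a small differential shift. It is no evidence that one would occur.

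**The case against.** A reader might infer that the form tells participants their arm. The documents do not go that far. They show neither the title as displayed nor the items, nor what participants are told the name EaseVRx means. The name is in the trial title and in exclusion criterion 6, so all arms may know it simply as the study product. Participants are at home, one per household under the synopsis, and cannot see that others receive no such form. This stands: the supportable wording is that the form could reveal active assignment.

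A reader might also infer that the form unmasks whichever section is followed. Under 14.1, Sham participants receive nothing and get no direct signal. Under 11.5, the claim would depend on items nobody reading the protocol can see. This stands too.

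On the contradiction, one can argue that 14.1 is the specific rule, that 9.1 agrees with it if the instruments are the same, and that footnote 5 is weak evidence because it also serves the device-use row. That narrows the conflict largely to 11.5, but the week-16 entry there still names two arms where 14.1 allows one.

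On the stakes, the primary endpoint and the protocol's secondary aims are measured at end of treatment, the protocol treats later visits mainly as exploratory, and claims data are not self-reported. This limits the consequence. It does not remove it, since SAP 1.2 calls long-term follow-up a secondary evaluation.

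Finally, eight weeks of interactive 3D or passive 2D content, and a behavioral skills survey given to every arm, may already have suggested the assignment. The added effect of one more form is therefore uncertain. That is a reason for modest claims rather than for leaving an avoidable cue in place.

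**Conclusion.** The concern holds in a limited form. It is certain that the sections disagree on which arms receive the questionnaire, that no Day 56 order is fixed, and that the perceived-assignment item is missing from 11.5. Confidence in these is high.

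It is possible, with moderate confidence at most, that a product-named form restricted to the EaseVRx arms would reveal active assignment to some of about 500 participants ahead of seven self-reported visits. This assumes that the title is visible and recognised. Any resulting bias would be expected to favour EaseVRx, but its size cannot be derived from the documents.

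The stronger conclusion that the primary endpoint is compromised is not supported. The BPI is already listed first, and harm would require it to be completed after the form.

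This is a change that should be made because it is cheap and removes an avoidable threat to blinding. It is not a flaw that invalidates the primary analysis.

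**What to change.** Amend the protocol as follows.

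- **Recipients.** Reconcile 6.2, 9.1, 11.5 and 14.1 so that they name the same arms and occasions, and say whether the product-enhancement item in 9.1 is the same instrument.
- **Title and content.** Use a neutral title such as VR user experience, with generic items, in all four arms at Day 56 and in both on-demand arms at week 16. Alternatively, hold EaseVRx-specific items until participants are unblinded.
- **Order.** Add perceived assignment to 11.5 and lock the Day 56 sequence in the portal: BPI, other patient-reported outcomes, perceived assignment, user experience last.

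The cost is a short amendment and a portal configuration change. Sham participants answer one more form, and feedback on product features becomes more generic or arrives later. Usability and satisfaction are still captured in all arms by the System Usability Scale and the satisfaction survey.
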